5.2 Exclusion Criteria Yes/No (Response of "yes" = patient ineligible)

- 5.2.1 _____ Metastatic breast cancer.
- **5.2.2** Planned surgery during the 15-week study period.

- **5.2.3** ALT/AST > 3x ULN or bilirubin > 1.5x ULN. If known Gilbert's syndrome, bilirubin may not be > 2x ULN (obtained ≤ 28 days of registration).
- **5.2.4** Clinically significant laboratory abnormalities, including: Creatinine >1.5 x ULN or Hemoglobin <9 g/dL (obtained \leq 28 days of registration).
- 5.2.5 _____ History of or currently has suicidal ideation or attempted suicide
- 5.2.6 _____ History of seizure other than febrile seizures in childhood.
- **5.2.7** Current use of valproate or clobazam. If patient takes valproate or clobazam, should discontinue 7 days prior to enrollment.
- **5.2.8** Use of cannabidiol, THC, or marijuana (oral, inhaled, or topical) within the 6 weeks prior to enrollment.
- **5.2.9** Known allergy or hypersensitivity to CBD or any of the excipients in the medication, including sesame.
- **5.2.10** _____ Unable to take oral medications.
- **5.2.11** _____ Pregnant or breast feeding.
- **5.2.12** Any medical condition that would interfere with the absorption of study medication. Prior gastric bypass is permitted.
- **5.2.13** Concurrent medical or arthritis disease such as active rheumatoid arthritis or inflammatory arthritis that could confound or interfere with evaluation of pain or efficacy. Patients with osteoarthritis are eligible.
- **5.2.14** _____ Patients with a prior or concurrent malignancy whose natural history or treatment, in the opinion of the treating investigator, has the potential to interfere with the safety or efficacy assessment of the investigational regimen.

6 STRATIFICATION FACTORS

N/A

7 TREATMENT PLAN

7.1 Cannabidiol

7.1.1 How Supplied, Stored, Packaged and Labeled

Cannabidiol (EPIDIOLEX, Greenwich Biosciences) will be purchased from commercial supply and stored in the University of Michigan Research Pharmacy. The Research Pharmacy will dispense one bottle per patient at the baseline study visit; if the patient is unable to come to clinic for the baseline visit then the medication will be mailed to the patient and the study medication log will be mailed or emailed to the patient. A second bottle

will be provided at the week 8 study visit; if the patient is unable to come to clinic for the 8 week visit then the medication will be mailed to the patient and the study medication log will be mailed or emailed to the patient.

EPIDIOLEX is a strawberry flavored clear, colorless to yellow solution supplied in a 105 mL amber glass bottle with a child-resistant closure containing 100 mL of oral solution (NDC 70127-100-01). Each mL contains 100 mg of cannabidiol. EPIDIOLEX is packaged in a carton with two 5 mL calibrated oral dosing syringes and a bottle adapter (NDC 70127-100-10). The pharmacy will provide 1 mL calibrated oral dosing syringes when doses less than 1mL are required.

Store EPIDIOLEX in its original bottle in an upright position at 20°C to 25°C (68°F to 77°F); excursions are permitted between 15°C to 30°C (59°F to 86°F). Do not refrigerate or freeze. Keep the cap tightly closed. The bottle with any unused drug will be returned to the study coordinator/Research Pharmacy at the completion of the trial.

7.1.2 Preparation and Administration

Patients should be instructed to take 25 mg (0.25 ml) twice a day approximately 12 hours apart for the first week, with food. Each week the patient should increase the dose by 25 mg twice a day until she reaches a maximum of 100 mg (1 ml) twice a day, unless she has difficulty tolerating the medication. If a dose is missed the patient should take it as soon as she remembers, although if it has been more than 8 hours she should not double up on dosing. If a dose is vomited it should not be made up.

The drug should be drawn up into a dry syringe. If the syringe is wet, it can make the drug appear cloudy; this does not affect its safety or efficacy.

Patients will be advised not to drive or operate machinery until they have gained sufficient experience on the study drug to gauge whether it adversely affects their ability to drive or operate machinery. Participants will be advised that concomitant use of alcohol or other CNS depressants may increase sedation and somnolence.

7.1.3 Accountability and Compliance

Study drug compliance during any period will be monitored by having the patient complete an IRBMED approved study drug diary.

7.2 Concomitant Medications and Therapies

7.2.1 Allowed Therapy

Patients are permitted to take concomitant aromatase inhibitor therapy, LHRH agonist therapy, anti-HER2 directed therapy, CDK4/6 inhibitor therapy, and/or anti-osteoclast therapy. Patients are permitted to use vaginal estrogen preparations.

Because of the potential for drug-drug interactions, consider a reduction in dosage of sensitive CYP1A2, CYP2B6, CYP2C8, CPY2C9, CYP2C19, and P-gp substrates, as clinically appropriate (see https://drug-interactions.medicine.iu.edu/MainTable.aspx and the drug prescribing information).

Patients who are taking opioids, NSAIDs, acetaminophen, duloxetine, gabapentin, and/or pregabalin at the time of study drug initiation should continue to take the same dose of medication for the 15 week study duration.

7.2.2 Prohibited Therapy

Patients with a history of hormone receptor positive breast cancer should avoid taking systemic or transdermal estrogen products (vaginal estrogen preparations are permitted).

Patients should not take valproate or clobazam while participating on this clinical trial.

7.3 **Duration of Therapy**

Patients will be treated with the study drug for 15 weeks (+/- 7 days).

7.3.1 Criteria for discontinuation of treatment ("off study")

The following will result in study treatment discontinuation:

- Discontinuation of AI therapy, defined as:
 - Discontinuation of the currently prescribed AI therapy for more than 7 days
- Evidence of new cancer or cancer recurrence
- Unacceptable toxicity (see section 8.1)
- Delay of 14 consecutive days of study treatment (CBD) due to any reason
- The participant may discontinue study treatment (CBD) at any time for any reason including participant request to be withdrawn from study
- Death

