AIMSS can lead to early treatment discontinuation in one-fifth of patients, which can increase risk of breast cancer recurrence by 45-50%.^{4, 14-16} Despite well-established clinical benefits of long-term AI treatment, more than 20% of patients discontinue AI therapy prematurely, primarily because of toxicity of therapy. While the primary toxicity of therapy is AIMSS, AI-treated women also report bothersome vasomotor and gynecologic symptoms, as well as insomnia, fatigue, anxiety, and depression. In addition, studies have shown an increase in inflammatory markers in patients with co-existing symptoms, supporting an underlying inflammatory mechanism.¹¹ Discontinuation of AI therapy before the recommended 5-10 years has been shown to increase risk of cancer recurrence and mortality.¹⁴⁻¹⁶ Therefore, well-tolerated and effective interventions to improve AI-associated symptoms, primarily AIMSS, are urgently needed.

Cannabinoids

Cannabinoids produce analgesia in patients with pain.¹⁷ These compounds, such as cannabidiol (CBD) and Δ^9 -tetrahydrocannabinol (THC), act on cannabinoid receptors 1 and 2 (CB1 and CB2) and other receptors in the endocannabinoid system, which are involved in complex behaviors and responses such as pain, sleep, and mood.¹⁸⁻²⁰ THC's activation of CB1 receptors is primarily responsible for the psychoactive effects that characterize cannabis intoxication.^{21, 22} In contrast to THC, CBD is non-intoxicating

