5 ELIGIBILITY CRITERIA

5.1 Inclusion Criteria Yes/No (Response of "no" = patient ineligible)

- **5.1.1** Female subject aged ≥ 18 years who is postmenopausal according to standard clinical criteria (see section 8.3) or who has been receiving concomitant LHRH agonist therapy.
- **5.1.2** Taking the currently prescribed aromatase inhibitor therapy (anastrozole, exemestane, or letrozole) for adjuvant treatment of breast cancer or for chemoprevention for at least 3 weeks and no more than 2 years at the time of enrollment.
- **5.1.3** Planning to take the same AI therapy for at least 15 weeks.
- **5.1.4** New or worsening joint pain and/or myalgias since starting the AI therapy, with *worst* pain score of at least 4 out of 10 on the BPI over the 7 days prior to enrollment.
- **5.1.5** Completion of surgery (mastectomy or lumpectomy/partial mastectomy) for treatment of breast cancer at least 3 months prior to enrollment. Completion of axillary surgery as indicated (not required).
- **5.1.6** Completion of chemotherapy, if given. Concurrent use of LHRHa therapy, anti-HER2 therapy, bisphosphonate therapy, PARP inhibitor therapy, and CDK4/6 inhibitor therapy is permitted.
- **5.1.7** Patients receiving treatment with NSAIDs, acetaminophen, opioids, duloxetine, gabapentin, and/or pregabalin must have been taking a stable dose for at least 30 days prior to enrollment if they plan to continue the drug during study participation. If they do not plan to take the medication during study participation, they should stop the medication at least 7 days before initiation of study treatment.
- **5.1.8** _____ ECOG Performance Status 0-2.
- **5.1.9** Able to self-complete questionnaires in English.
- **5.1.10** Able to provide informed consent and willing to sign an approved consent form that conforms to federal and institutional guidelines.

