9 STUDY CALENDAR

Required Studies	Screening ª	Baseline ^b	Weeks 1, 2, 3 (+/- 2 days) ^c	Weeks 4, 6 (+/- 2 days) ^c	Week 8 (-2, +7 days) ^c	Week 12 (+/- 2 days) ^c	Week 15 (-2, +7 days) ^{c, j}	Off Study (if prior to week 15) ^d
Informed consent	Х							
Medical History	Х							
Performance status ^m	Х							
Study visits ⁱ	Xd	Х			Х		Х	Х
Study coordinator phone calls ^{k, n}			Х	Х	Х	X	XI	XI
Vital signs ^e	Х							
Concomitant medications	Х	Х						
Adverse event assessment			Х		Х		Х	Х
Patient reported questionnaires ^f								
- BPI	Х	Х	Х	Х	Х	Х	Х	Х
- PROMIS		Х		X (wk 4 only)	Х		Х	Х
- GRC			X°	X (wk 4 only)	Х	Х	Х	Х
- METE		Х						
- FM Survey		Х					Х	Х
- CSQ		Х					Х	Х
- PANAS		Х					Х	Х
- PHQ9 ^p	Х	Х						
Phlebotomy ^g								
- Research	X ^r X				X X		Х	X X
 Clinical labs (aspartate aminotransferase, alanine aminotransferase, total 	X			X (wk 4 only)	Х		X	X
bilirubin, serum creatinine, complete blood count)								
Al therapy (standard of care)								•
Dispense study medicine		Х			Х			
CBD treatment ^h								
Medication log		Х			Х		Xi	Xi

a. Screening and baseline visits can take place on the same day. The informed consent can be completed either in person or remotely using SignNow. The BPI and PHQ9 will be completed after signing the ICF and can be completed by phone or electronically. Screening clinical lab studies must be completed within 28 days of registration; if they have already been completed for another reason (other than participating in this clinical trial) they do not need to be repeated.

b. Baseline visit can take place up to 4 weeks after the screening visit. Patient does not need to be seen by physician or advanced practice provider.

c. Timed based on initiation of CBD therapy.

d. This is the visit conducted at the time of AI discontinuation and/or study drug discontinuation as per section 7.3.1. These questionnaires should be completed within 3 business days of medication discontinuation. Patients will return remaining study drug and medication log at that study visit or at their next routine clinic

visit. Also if a patient discontinues study drug early, she should continue to complete questionnaires according to the study calendar through the 15 week timepoint.

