k. Study coordinator calls are to assess adverse events including suicidality and (if applicable) determine if there is a reason that the patient should not increase the dose by one dose level (as per section 8.1.1). If there is a question about whether the patient should or should not increase the dose, the study coordinator will contact the PI or Co-I. Also if patients have not completed questionnaires or if they decline to complete questionnaires electronically, the study coordinator should ask the questions by phone.

I. The study coordinator should follow-up with the patient by phone 30 days following the off-study visit to assess resolution of any AEs as per section 16.5. m. Performance status assessment at screening will be performed by a licensed physician (or physician's assistant or nurse practitioner) or registered nurse. Can have been performed up to 28 days before the screening visit, and can be performed during a virtual visit.

n. The study coordinator will ask about suicidal ideation on the phone calls using question 9 from the PHQ9: "How often have you been bothered by the following in the past week: Thoughts that you would be better off dead, or thoughts of hurting yourself in some way? Not at all, several days, more than half the days, nearly every day". If a patient reports anything other than "Not at all" to the question, the patient's oncology treatment team will be notified and the patient will be managed according to usual clinical protocols. If the treatment team is not available, the PI or another of the co-Is will be notified.

o. GRC should be completed at week 2.

p. The study coordinator should review the response to PHQ9 question 9 prior to dispensing the study medication to the patient. If the answer to the question is anything other than "Not at all", the study medication should not be dispensed and the patient's clinical team or covering provider should be notified immediately.

q. The screening study visit can be conducted virtually if the necessary patient information (other than lab results) can be found in the medical chart. Patient will need to undergo phlebotomy prior to enrollment in the study if screening lab studies have not otherwise been performed within the past 28 days.

r. If clinical lab studies do not need to be performed at screening because they have been performed within the 28 day window, the research blood specimens at screening can instead be collected at baseline.

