12.3.2 Secondary endpoints

- 1. The proportion of patients who have at least a 2 point reduction in *worst* pain from baseline to 15 weeks will be reported with the corresponding exact binomial confidence interval.
- 2. The proportion of patients who have at least a 2 point reduction in *average* pain from baseline to 15 weeks will be reported with the corresponding exact binomial confidence interval. Differences from baseline at each time point for average pain and pain interference will be summarized via mean and standard deviation. Patient reported outcomes will be analyzed using linear mixed effects models and include a subject-specific random effect to account for the natural heterogeneity across patients. Normalizing transformations will be used if necessary to ensure accurate model fit.
- 3. Differences from baseline at each time point for all other patient reported outcomes (sleep disturbance, fatigue, physical function, anxiety, depression, and cognitive function over time) will be summarized via mean and standard deviation. Patient reported outcomes will be analyzed using linear mixed effects models and include a subject-specific random effect to account for the natural heterogeneity across patients. Normalizing transformations will be used if necessary to ensure accurate model fit.
- 4. Safety will be assessed throughout the trial and adverse events will be reported using descriptive statistics and stratified by dose.
- 5. We will report the proportion of individuals with undetectable levels of estradiol at baseline and 15 weeks with corresponding exact binomial 95% confidence intervals. The exact levels of estradiol at baseline and 15 weeks will be summarized using descriptive statistics.

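### AI intake is not recorded after baseline, so a rise in week-15 estradiol cannot be assigned to CBD or to missed AI doses

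*Combined protocol and SAP*

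**What the plan says.** Intake of the study drug is followed closely. Section 7.1.3 states: "Study drug compliance during any period will be monitored by having the patient complete an IRBMED approved study drug diary". Footnote i of the Section 9 calendar adds the return of medication log #1 at week 8, and of log #2 with the remaining drug at week 15.

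The AI appears in four places:

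- **Entry.** Section 5.1.2 requires 3 weeks to 2 years on the current AI. Section 5.1.3 requires "Planning to take the same AI therapy for at least 15 weeks".
- **Calendar.** AI therapy is a row labelled as standard of care. The concomitant medications row is marked at screening and baseline only.
- **Calls.** Footnote k says: "Study coordinator calls are to assess adverse events including suicidality". It goes on to the CBD dose step and uncompleted questionnaires, and does not mention the AI.
- **Stopping.** Section 7.3.1 ends study treatment on "Discontinuation of the currently prescribed AI therapy for more than 7 days". Footnote d describes the off-study visit: "This is the visit conducted at the time of AI discontinuation and/or study drug discontinuation as per section 7.3.1".

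For the endpoint, Section 12.3.2 (secondary, item 5) says: "We will report the proportion of individuals with undetectable levels of estradiol at baseline and 15 weeks". Estradiol levels are also summarised at both times, and exploratory item 3 does the same for estrone and estrone sulfate. Section 12.3 contains no AI-adherence covariate, sensitivity analysis or rule for AI interruption.

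**The concern.** Section 2.2 explains that AIs block estrogen synthesis. AI intake therefore directly determines the quantity that the estradiol objective measures. The trial asks whether CBD changes circulating estrogen in women whose treatment depends on keeping it low, so a patient who becomes detectable at week 15 is the result that would matter most. If she had also missed AI tablets before the draw, the planned data would not show it, and there is no control arm to show how often this happens without CBD.

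Section 7.3.1 does not close the gap. Interruptions of 7 days or less, even repeated ones, trigger neither a visit nor a record. Such an interruption could fall just before the week-15 draw or span the full 7-day recall of the week-15 BPI.

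The same missing record bears on worst pain, with much weaker support. The AI is the presumed cause of the pain being treated, and Section 2.2 lists loss of estrogen's pain-relieving action among the postulated mechanisms.

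**Working it through.** **1. The plan's own figure.** Section 12.2 gives 40 evaluable patients, two-sided 5%, SD 3 and standardized effect 0.45, for 80% power. The difference is 0.45 × 3 = 1.35, stated as 1.4 points. A one-sample t-test at n = 40 and effect 0.45 has 79.3% power (81.2% by normal approximation). The figure reproduces, and this point does not affect it.

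**2. Where each drug is recorded.**

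| | CBD | AI |
|---|---|---|
| At entry | not applicable | 5.1.2, 5.1.3 |
| Daily record on treatment | diary and logs (7.1.3, footnote i) | none described |
| Scheduled calls | dose step (footnote k) | not mentioned |
| Concomitant medications after baseline | not applicable | not scheduled |
| Interruption rule | 14 consecutive days (7.3.1) | more than 7 days (7.3.1) |
| Use in Section 12.3 | adverse events by dose | none |

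**3. Estradiol.** Assume all 40 evaluable patients have an assay at both times. One patient moving from undetectable to detectable changes the proportion by 1/40 = 2.5 points. The documents give neither the baseline proportion nor the rate of missed doses, so the rows below are illustrations, with exact (Clopper-Pearson) 95% intervals:

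| Undetectable | Proportion | 95% CI |
|---|---|---|
| 40/40 | 100% | 91.2 to 100 |
| 38/40 | 95% | 83.1 to 99.4 |
| 36/40 | 90% | 76.3 to 97.2 |
| 34/40 | 85% | 70.2 to 94.3 |

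If 38/40 were undetectable at baseline, and 10% of patients (4 of 40) became detectable through missed AI doses, week 15 would show 34/40: 4 × 2.5 = 10 points lower. Four patients made detectable by CBD would give the same row.

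**4. Worst pain, under assumptions only.** Suppose k of 40 patients have an AI gap at week 15 but not at baseline, each with a fall of e points, and CBD has no effect. The mean shift is k × e / 40. The last column is the chance of a significant result with SD 3 and n = 40 (nominal 5%).

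| k | e | Shift | Share of 1.4 | P(significant) |
|---|---|---|---|---|
| 2 (5%) | 1 | 0.05 | 4% | 5.1% |
| 4 (10%) | 2 | 0.20 | 14% | 7.0% |
| 4 (10%) | 3 | 0.30 | 21% | 9.5% |
| 8 (20%) | 3 | 0.60 | 43% | 23.5% |

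For scale, the standard error of the mean change is 3/√40 = 0.47. Both k and e are assumed, and so is the sign of e.

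**The case against.** The strongest objection concerns pain. A reader might infer that missed AI tablets ease joint pain within days and create a false CBD benefit in the primary endpoint. The documents do not support that:

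- **Time scale.** No section says that a gap of 7 days or less relieves pain. Section 2.2 has symptoms emerging over about 3 months and peaking at 6, calls the etiology poorly understood, and offers estrogen loss only as a postulated mechanism.
- **Rate.** The background statement that "more than 20% of patients discontinue AI therapy prematurely, primarily because of toxicity of therapy" refers to therapy intended to last 5 to 10 years. It is not a 15-week rate and does not describe short gaps.
- **Direction.** The endpoint is change from baseline, so habitual skipping partly cancels. Entry requires worst pain of at least 4, so pain-driven skipping could be greatest at baseline. If CBD helped, AI intake could improve, which would work against CBD.
- **Size.** A 2 to 3 point fall from a short gap exceeds the trial's whole 1.4-point target.

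All of this stands, and it makes pain a secondary concern.

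A reader might also infer that AI gaps leave no trace anywhere. That goes too far. The case report forms and diary template are not in the documents, stops of more than 7 days lead to an off-study visit, and Section 16.4 has quarterly meetings that review adherence to the protocol. What can be said is that the protocol calls for no such record.

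Finally, estradiol is descriptive, with no test or decision rule, and a single arm cannot firmly attribute any change. Vaginal estrogen, permitted in 7.2.1, is another possible source, and its use is likewise not scheduled for recording after baseline. True, but the AI is the one drug known from the protocol itself to act on this endpoint, and its intake cannot be reliably reconstructed later.

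**Conclusion.** The concern holds for estradiol. As planned, a detectable or higher week-15 value cannot be assigned to CBD or to missed AI doses, and each such patient moves the undetectable proportion by 2.5 points if 40 patients are assayed. How many patients would be affected is unknown, because the documents give no missed-dose rate and do not say how long a gap makes estradiol detectable. The conclusion rests on the protocol's own account of AI action, the single arm, and the absence of any described AI record after baseline; a case report form field outside the documents would weaken it.

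For worst pain, an effect is possible but its size and direction are unknown. The span of 0.05 to 0.6 points is an illustration and should not be read as an estimate of bias. The sample size and the primary analysis stand. The change should be made because it is cheap and the information has to be collected prospectively.

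**What to change.** Leave 7.3.1 unchanged.

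**Data collection**
- Add a daily AI-taken tick to the medication log that patients already keep, or one question on missed AI doses at the scheduled coordinator calls.
- Record AI doses missed in the prior 7 days at baseline, week 8 and week 15, for both the blood draw and the BPI. The baseline question is needed because the log starts with CBD. Where the first research sample is taken at screening (footnote r, Section 15.2.1), ask it there too.

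**Section 12.3**
- Keep the all-patient analyses as primary.
- Report AI intake descriptively at baseline and week 15.
- List the missed AI days for every patient whose estradiol becomes detectable.
- Give the changes in estradiol, estrone, estrone sulfate and worst pain among patients without recent AI interruption, as a supportive sensitivity analysis only. State that this subset is selected on post-baseline behaviour, which CBD benefit or toxicity may influence, and so cannot replace the all-patient result.

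**Cost.** One log column or one scripted question, a short item at three time points, and one extra table. Patient burden is small. Patients with recent AI interruption drop out of the sensitivity analysis only.
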